7.2.2.2.1.1. Instructions for Insulin Self-administration

Patients will administer their basal insulin QD dose subcutaneously (in the abdomen, upper arm, or thigh) at any time of the day approximately the same time every day from the following day after Visit 2. Patients should be trained by the site personnel on how to inject study insulin and to rotate site injections, following good practices for insulin administration before the first injections (Visit 2).

Patients will be instructed to monitor themselves for any signs and symptoms of immediate or delayed hypersensitivity or allergic reactions following their injections. Patients will be instructed to contact emergency medical services in case of severe reactions.

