9.5. Selection and Timing of Doses

All treatments will be administered according to the country-specific product labeling where applicable. Insulin lispro should be administered subcutaneously within 15 minutes before meals or immediately after the meal. LY2963016 and Lantus® are to be administered QD by the patients at bedtime or anytime of the day (but approximately the same time of the day) every day from the following day after Visit 2. Investigators are advised to take into account patients'

mealtimes and timing of the BG readings in making adjustment decisions on insulin dose or in requesting additional BG monitoring. For example, if a patient's evening meal is late and bedtime is only an hour later, the investigator should exercise caution in making insulin-dose adjustments to attain glycemic targets and to prevent nocturnal hypoglycemia.

The investigator will guide the patient in adjusting the insulin doses based on the SMBG profiles during the study to achieve preprandial BG targets of 79 to 126 mg/dL (4.4 to 7.0 mmol/L) while minimizing hypoglycemia.

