12.2.10. Subgroup Analyses

The consistency of the treatment effect will be assessed in the following subgroups in the FAS if there are a sufficient number of patients in each treatment by subgroup:

- entry HbA1c levels (<7%, ≥7%)
- entry HbA1c levels (<8.5%, ≥8.5%)
- prestudy treatment (Lantus®-bolus, other basal-bolus, premixed insulin)
- entry BMI (<30, ≥30)
- entry age (<65, ≥65)
- Prestudy metformin or acarbose use (metformin only, acarbose only or neither)
- Renal function, as estimated by estimated glomerular filtration rate (EGFR). The following EGFR categories will be used:
 - normal or increased GFR: EGFR (≥90 mL/min/1.73 m²)
 - mild reduction in GFR: EGFR (60 to 89 mL/min/1.73 m²)
 - Moderate reduction in GFR: EGFR (30 to 59 mL/min/1.73 m²)
 - Severe reduction in GFR: EGFR (15 to 29 mL/min/1.73 m²)
 - Kidney failure: EGFR (<15 mL/min/1.73 m²).

The change in HbA1c from baseline to 24-week endpoint will be analyzed using MMRM with treatment, visit, prestudy treatment, prestudy metformin or acarbose usage, subgroup, subgroup-by-treatment interaction, subgroup-by-visit interaction, treatment-by-visit interaction, and treatment-by-visit-by-subgroup interaction as fixed-effects, the baseline value of HbA1c as a covariate, and a random effect for patient for the FAS. If the subgroup is one of the stratification variables, then the subgroup will only be included once in the model. A significant treatment-by-subgroup interaction ($p < .05$) may be indicative of a differential treatment effect across levels of the subgroup, necessitating further exploration of the nature of the interaction.

Other subgroup analyses may be performed if deemed appropriate as exploratory analyses.

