Attachment 5. ABES General Rules and Guidance for Intensive Insulin Therapy for ABES Study

1. Target glycemic goals would be the same for all patients (HbA1c <7%, preprandial capillary BGs: 79 to 126 mg/dL ([4.4 to 7.0 mmol/L], avoiding hypoglycemia).
2. Study treatment will start on the second day of randomization (Visit 2). At randomization, in the patients who were administered with basal-bolus therapies before enrollment with QD basal insulin and mealtime insulins will receive instruction to start new regimen with either QD LY2963016 or insulin glargine as basal insulin at the same doses next day. For those patients with BID prestudy basal as a part of basal-bolus regimen, the total daily prestudy basal insulin dose will be reduced by 20%, therefore, the study basal insulin dose will be 80% of the prestudy basal insulin dose. Insulin lispro will be administered with meals at the same doses as the patient's prestudy mealtime insulin dose while avoiding hypoglycemia, as determined by unit-to-unit conversion.

In the patients who were administered with premixed insulin will stick to prestudy regimen on the day of randomization, the total daily dosage at randomization will be the average for the sum of all insulin doses taken in the 3 days prior to randomization. The total daily dosage will then be split between basal and bolus insulin doses at the discretion of the investigator. For the treatment regimen, the initial basal insulin dose should be approximately 40% to 60% of the total daily dose. Then the initial bolus insulin dose (insulin lispro, 60% to 40% of the total daily dose) will be divided into 3 equal doses before 3 meals (or appropriate adjustment at investigator's discretion). The group of patients will be instructed by the investigators for receiving treatment with basal-bolus insulins in the trial.

The following examples are provided as a dose calculation tool of conversion from prestudy insulins to trial drugs.

Examples:

Patients will stick to pre-study insulin regimen at Visit 2, and new insulin regimen will start on the next day after visit 2.

- a. Prestudy basal-bolus insulin regimen (QD basal + TID premeal) (1:1 conversion of basal-bolus insulin):

Lantus® 12U QD + Humulin R 6U (breakfast), 4U (lunch), 5U (dinner)

Will switch to:

LY2963016 (or Lantus®) 12U QD (same dosing time as previous) + Lispro 6U (breakfast), 4U (lunch), 5U (dinner)

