- b. Prestudy basal-bolus insulin regimen (BID basal + TID premeal) (1:1 conversion of bolus insulin and 80% of pre-study basal insulin):

NPH 10U (breakfast), 10U (dinner) + Lispro 6U (breakfast), 6U (lunch), 6U (dinner)

Will switch to:

LY2963016 (or Lantus®) $(10U+10U)*80%=16U$ QD (daytime or evening/bedtime at the discretion of investigator) + Lispro 6U (breakfast), 6U (lunch), 6U (dinner).

- c. Prestudy premixed insulin BID

In past 3 days, Humulin 70/30 18U (breakfast), 12U (dinner), total daily insulin dose: 30U

Will switch to:

LY2963016 (or Lantus®) $30U*40%=12U$ QD (daytime or evening/bedtime at the discretion of investigator) +6U for each meal ($30U*60%=18U$, equally divided into 3 meals), or appropriate adjustment at discretion of the investigators.

3. Insulin dose adjustments are mostly based upon SMBG levels. Four-point SMBG values will be reviewed during the telephone visit period and be recorded in the eCRF during the next investigator-site visit. In addition, 7-point SMBGs are also recorded during the 1-week period preceding office visits. The patient's SMBG results are to be used by the investigator to inform dose adjustments for a particular insulin dose (that is, adjustment based on glucose pattern or trends), as represented in Table A5.1.

Table A5.1. Overview of Scenarios with Different Blood Glucose Levels and Corresponding Insulin-dose Adjustments*

Time	BG <80 mg/dL (<4.4 mmol/L)	BG >140 mg/dL (>7.8 mmol/L)
AM	Decrease Basal or Bedtime insulin	Increase Basal or Bedtime insulin
Pre-midday meal	Decrease AM lispro	Increase AM lispro
PM	Decrease Pre-midday meal lispro	Increase Pre-midday meal lispro
	Bedtime BG <100 mg/dL (<5.5 mmol/L)	Bedtime BG >160 mg /dL (>8.9 mmol/L)
BEDTIME	Decrease PM lispro	Increase PM lispro

Abbreviations: BG = blood glucose.

* Adapted from Staged Diabetes Management.

Additional BG monitoring may be requested by the investigator while optimizing insulin doses. The investigator may adjust the insulin dose every 3 to 4 days (twice per week, [for example, via instructions to patient]) when appropriate, based on the patient's glycemic needs as reflected by SMBG measurements, and after the investigator has evaluated the role of diet and exercise on the resulting BG measurements.

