5.2.12. Subgroup Analyses

The consistency of the treatment effect for the change in HbA_{1c} level will be assessed in the following subgroups in the FAS population if there are sufficient numbers of patients in each treatment by subgroup (e.g. 20 patients per cell):

- Entry HbA_{1c} levels (<7%, ≥7%)
- Entry HbA_{1c} levels (<8.5%, ≥8.5%)
- Pre-study treatment (Lantus[®]-bolus, other basal-bolus, premixed insulin)
- Entry BMI (<30, ≥30)
- Entry BMI (<25, ≥25)
- Entry age (<65, ≥65)
- Entry age (<75, ≥75)
- Gender
- Prestudy metformin or acarbose use (metformin only, acarbose only or neither)
- Time of basal insulin injection (daytime, evening/bedtime)
- Renal function, as estimated by estimated glomerular filtration rate (EGFR) using the MDRD formula (see [Appendix 2](#)). The following EGFR categories will be used:

- normal or increased GFR: EGFR (≥ 90 mL/min/1.73 m²)
- mild reduction in GFR: EGFR (60 to 89 mL/min/1.73 m²)
- Moderate reduction in GFR: EGFR (30 to 59 mL/min/1.73 m²)
- Severe reduction in GFR: EGFR (15 to 29 mL/min/1.73 m²)
- Kidney failure: EGFR (< 15 mL/min/1.73 m²).

The categories severe reduction in GFR and kidney failure will be combined if there are fewer than 20 patients in either of these categories.

The change in HbA_{1c} from baseline to 24-week endpoint will be analyzed using MMRM with treatment, visit, prestudy treatment, prestudy metformin or acarbose usage, subgroup, subgroup-by-treatment interaction, subgroup-by-visit interaction, treatment-by-visit interaction, and treatment-by-visit-by-subgroup interaction as fixed-effects, the baseline value of HbA_{1c} as a covariate, and a random effect for patient for the FAS population. If the subgroup is one of the stratification variables, then the subgroup will only be included once in the model. A significant treatment-by-subgroup interaction ($p < .05$) may be indicative of a differential treatment effect across levels of the subgroup, necessitating further exploration of the nature of the interaction.

The contrast from the MMRM model with the OM option using PROC Mixed in SAS above will be used to obtain the LSmeans for change in HbA_{1c} levels from baseline to Week 24 within each treatment at each level of the subgroup. Additionally, the difference of these LSmeans between treatment groups with 95% confidence interval and p-values will be presented.

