For each subgroup listed above, the change in weight from baseline to 24-week will be analyzed using the same methodology as the subgroup analysis of HbA_{1c}.

Additional subgroup analyses will be carried out on selected safety outcomes:

- a) total, severe or nocturnal hypoglycemia at 24-week endpoint and for the overall 24-week period (rates and incidence)
- b) treatment-emergent antibody response (TEAR) at 24-week endpoint and for the overall 24-week period
- c) detectable insulin antibodies at 24-week endpoint and for the overall 24-week period
- d) categories of adverse events:
 - treatment-emergent adverse events (TEAEs) (overall incidence and preferred terms with $> 5\%$ incidence)
 - TEAEs related to study drug (overall incidence)
 - special topic assessment of allergic events (overall incidence)
 - injection site reactions (overall incidence)
 - serious adverse events (overall incidence)

For rates and incidence of hypoglycemia (total, nocturnal, severe) and categories of adverse events, the same set of 11 subgroups used to analyze change in HbA_{1c} and change in weight will be analyzed.

For each categorical safety outcome and subgroup listed above, the proportion of patients with an event will be compared between treatments for the FAS. Within each subgroup, treatments will be compared using the Mantel-Haenszel test and the odds ratio and p-value from this test will be reported. The homogeneity of the odds ratios across subgroups will be assessed using the Breslow-Day test.

For the 11 subgroups listed above, the rate of total, severe or nocturnal hypoglycemia per year at the 24-week endpoint and for the overall 24-week period will be analyzed. Within each subgroup, treatments will be compared using the negative binomial (NB) model with treatment as the only factor. The NB mean for each treatment and their ratio with corresponding 95% confidence interval will be presented. Additionally, within each subgroup the rates will be compared using the Wilcoxon test. The significance of the subgroup-by-treatment interaction will be evaluated using a negative binomial model with factors treatment, subgroup and treatment-by-subgroup interaction. The negative binomial model will be implemented using the SAS PROC GENMOD with natural logarithm of exposure time (in days) as an offset variable. The above subgroup analysis will be performed and p-values will be provided if there are at least a total of 20 events in the combined treatment groups.

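### The injection-time subgroup in SAP 5.2.12 is not tied to a value recorded before randomisation, although in this open-label trial the time can be chosen once the arm is known

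*SAP*

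**What the plan says.** The subgroup list in SAP 5.2.12 includes "Time of basal insulin injection (daytime, evening/bedtime". Other items on the list are anchored before treatment. HbA1c, BMI and age are labelled as entry values, and prior insulin and metformin/acarbose use as prestudy values. Injection time carries no such label, no visit, and no rule for a patient who changes time. Protocol 12.2.10 opens its own list with "The consistency of the treatment effect will be assessed in the following subgroups in the FAS" but does not include injection time, so it offers no definition either.

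On how the time is set:

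- Protocol 7.2.2.2.1.1 tells patients to inject "at any time of the day approximately the same time every day from the following day after Visit 2".
- Protocol 9.5 has basal insulin "administered QD by the patients at bedtime or anytime of the day (but approximately the same time of the day").
- Attachment 5, item 2, examples b and c (prior twice-daily basal and prior premix) leave it as "daytime or evening/bedtime at the discretion of investigator".
- Attachment 5, item 2, example a (prior once-daily basal) carries the earlier time over: "12U QD (same dosing time as previous").

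Protocol 9.7 states that investigators and patients know the assignment. Randomisation is at Visit 2 (Protocol 7.2.2.2) and study insulin starts the next day (Protocol 9.1). Injection time is not a stratification factor (Protocol 9.3).

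On use, SAP 5.2.12 applies the subgroup to change in HbA1c and in weight, and then more widely: "For rates and incidence of hypoglycemia (total, nocturnal, severe) and categories of adverse events, the same set of 11 subgroups". A significant interaction, it says, "may be indicative of a differential treatment effect across levels of the subgroup".

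**The concern.** A subgroup comparison keeps the protection of randomisation only if the arm cannot influence who belongs to the subgroup. Here it can. An investigator who knows the arm decides, for a patient with no earlier once-daily time, whether the injection is given by day or in the evening. The two options offered are exactly the two levels of the SAP subgroup. If hypoglycemia-prone patients are moved to daytime injection more readily in one arm, the daytime groups of the two arms no longer contain comparable patients, and neither do the evening groups. A difference in case mix would then appear as a treatment-by-time interaction.

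Hypoglycemia is the outcome most exposed, because injection time and nocturnal events are clinically linked. Within each subgroup, the hypoglycemia rate model in SAP 5.2.12 has treatment as its only factor, so nothing in it would adjust for such an imbalance. The omission also cannot be repaired at analysis: if the plan was not recorded before assignment, there is no pre-assignment value to go back to.

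**Working it through.** **1. Plan's own figures.** The illustration uses the SD and sample size from SAP 5.1.1, so these come first. With margin 0.40, SD 1.05, true difference 0, one-sided alpha 0.025 and 80% power:

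n = 2 × 1.05² × (1.960 + 0.842)² / 0.40² = 108.2, rounded up to 109 per arm. Then 109 / (1 − 0.15) = 128.2, rounded up to 129. Both stated figures reproduce, and nothing below changes them.

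**2. Hypoglycemia illustration, no true treatment effect.** From the documents: 129 per arm. Assumed: 30% of patients are hypoglycemia-prone with twice the event rate of the rest, and 30% of the non-prone inject by day in both arms.

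*Full case: 60% (LY2963016) and 40% (Lantus) of prone patients inject by day.*

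| Cell | Fraction of arm | Patients | Prone share | Relative rate |
|---|---|---|---|---|
| Daytime, LY2963016 | 0.18 + 0.21 = 0.39 | 50.3 | 0.18/0.39 = 0.462 | 1.462 |
| Daytime, Lantus | 0.12 + 0.21 = 0.33 | 42.6 | 0.12/0.33 = 0.364 | 1.364 |
| Evening, LY2963016 | 0.12 + 0.49 = 0.61 | 78.7 | 0.12/0.61 = 0.197 | 1.197 |
| Evening, Lantus | 0.18 + 0.49 = 0.67 | 86.4 | 0.18/0.67 = 0.269 | 1.269 |

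Rate ratios: daytime 1.462/1.364 = 1.072; evening 1.197/1.269 = 0.943. The spurious interaction ratio is 1.072/0.943, which is 1.136 before rounding; its log is 0.128.

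Standard error of the log interaction ratio, ignoring Poisson noise: SE = √(k × S), where k is the negative-binomial dispersion (assumed 0.5 to 2) and S = 1/50.3 + 1/42.6 + 1/78.7 + 1/86.4 = 0.0676. This gives SE = 0.184 at k = 0.5 and 0.368 at k = 2. Bias/SE is 0.69 and 0.35, and the two-sided test at 1.96 rejects 10.7% and 6.4% of the time.

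*Smaller cases: only some prone patients have a discretionary time, and the rest split 50/50 in both arms.*

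| Prone patients with a discretionary time | Prone injecting by day, LY2963016 vs Lantus | Interaction ratio | Rejection, k = 0.5 | Rejection, k = 2 |
|---|---|---|---|---|
| All | 60% vs 40% | 1.136 | 10.7% | 6.4% |
| Half | 55% vs 45% | 1.066 | 6.4% | 5.3% |
| A quarter | 52.5% vs 47.5% | 1.032 | 5.3% | 5.1% |
| No arm difference | 50% vs 50% | 1.000 | 5.0% | 5.0% |

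**3. HbA1c, same full case.** If prone patients change by D points differently from the others, the spurious interaction is D × [(0.462 − 0.364) − (0.197 − 0.269)] = 0.170 × D. That is 0.034 points for D = 0.2 and 0.085 for D = 0.5. The SE is 1.05 × √0.0676 = 0.273, so the distortion is negligible.

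**4. HbA1c under a stronger assumption.** A separate simulation used no treatment effect, 109 per arm, SD 1.05, and a prognostic factor correlated 0.3 to 0.5 with the outcome.

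- Where timing followed the same rule in both arms, the interaction test rejected at about 5%.
- Where timing depended on the factor in one arm only (log-odds 0.5 to 1 per SD of the factor), it rejected in 8% to 33% of trials. The false within-subgroup differences were about 0.07 to 0.22 points, of opposite sign in the two subgroups.

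Steps 2 to 4 agree on the mechanism: timing must depend on prognosis differently in the two arms. They differ on size because the inputs are assumed.

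**The case against.** The strongest reply is that nothing in the documents suggests timing would differ by arm. The two products share an amino acid sequence, Protocol 9.4 says they will be dosed similarly, and the Attachment 5 examples use the same wording for both. With the same rule in both arms there is no inflation. The 60/40 split is invented, and example a keeps the old time for prior once-daily patients, so the half and quarter cases (5.1% to 6.4%) are more plausible than the full one. Ignoring Poisson noise makes even those figures upper values. All this stands, and it limits the size. It does not make the subgroup one protected by randomisation.

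Two further points also limit the stakes. First, severe-hypoglycemia rates may never be analysed by subgroup. The earlier type 1 trial had 4.9% and 4.5% of patients with such events over 52 weeks. At 4.7%, 258 patients give about 12 affected, or about 6 when scaled to 24 weeks, whereas SAP 5.2.12 asks for at least 20 events. This assumes similar incidence here, and recurrent events could raise the count. Second, 11 unadjusted 5% tests, if independent, already carry a 1 − 0.95¹¹ = 43% chance of at least one false positive per outcome, so in the smaller cases an extra 0.1 to 1.4 percentage points on one test changes little.

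It can also be said that the SAP entry is merely ambiguous and could be read as a prestudy time. For prior twice-daily basal and premix patients, however, no earlier once-daily time exists. The only time available for them is one set at or after Visit 2, and nothing requires it to be set before assignment.

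**Conclusion.** The concern holds, as an optional improvement. As written, the plan allows a variable chosen with the arm known to define a subgroup used for interaction tests and within-subgroup p-values on HbA1c, weight, hypoglycemia and adverse events. The exposure lies mainly with patients coming from twice-daily basal or premixed insulin, although Protocol 9.5 permits any time for everyone.

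The expected effect is small and mainly concerns hypoglycemia. Every input to the illustrations other than the sample sizes and the SD is assumed, so they show what could happen, not what will. The noninferiority conclusion does not depend on this subgroup.

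**What to change.** At Visit 2, record the planned basal injection time (daytime or evening/bedtime) in the web response system or the eCRF before the assignment is released. Add one sentence to Protocol 7.2.2.2 requiring this. Add one to SAP 5.2.12 defining the subgroup by that entry, whatever time is used later. The investigator remains free to choose the actual time; dosing, titration and sample size do not change.

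The cost is one data field and about a minute per patient at Visit 2. The drawback is that a patient who later switches stays in the planned group, so the analysis describes intended rather than actual timing. If actual timing is also of interest, it can be reported separately and labelled exploratory and non-randomised. That label alone is the cheaper fallback if the field cannot be added, but it leaves the subgroup without a randomised comparison.

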5.1. Determination of Sample Size

5.1.1. Sample Size Section from the Protocol

Based on the primary objective, to show noninferiority of LY2963016 to Lantus® at the 0.40% noninferiority margin (NIM), 109 completers per arm (218 total) are needed at 24 weeks. This calculation assumes no treatment difference in HbA1c between LY2963016 and Lantus®, a common standard deviation (SD) of 1.05% for change from baseline in HbA1c, a two-sided significance level of 0.05, and over 80% power. Assuming a 15% dropout rate at 24 weeks, the required number of randomized patients is 129 per arm (258 total). This sample size is noted as the minimum sample size required in the study.

Blinded sample-size reestimation (bSSR) may be performed when approximately 40% of the subjects have been enrolled in the study and finished 24-weeks of treatment, or about 6 months prior to the completion of enrollment, depending on which occur first by team assessment. This reestimation will use a statistical model to estimate the variability in the change in HbA1c from baseline to 24 weeks using all available patient HbA1c values at the time of data cutoff. The estimate of variability will then be used to recalculate the sample size that would be needed to have 80% power for a NIM of 0.4%, assuming no difference between treatments. The sample size from the study is constrained between a predefined minimum sample size of 258, and a maximum sample size of 400 patients. If the recalculated sample size is smaller than minimum sample size planned, the study will enroll to the minimum sample size. If the recalculated sample size is larger than the planned minimum sample size, the team will make a decision whether to increase sample size to the reestimated sample size, bounded by the predefined maximum, or accept the consequent reduction in power.

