5.2.7. Primary Efficacy Outcome and Methodology

The primary efficacy outcome will be the change in HbA1c level from baseline to 24 weeks. The primary analysis will be a likelihood-based, MMRM approach, treating the data as missing at random (MAR) for the FAS population. The MMRM model will evaluate the change from baseline to each postbaseline visit in HbA1c level as the dependent variable with treatment (LY2963016, Lantus®), pre-study treatment (Lantus®-bolus, other basal-bolus, premixed insulin), and pre-study metformin or acarbose usage (metformin only, acarbose only, or neither), visit, and interaction between visit and treatment as fixed effects; the baseline value of HbA1c as a covariate; and a random effect for patient. The MMRM model will be carried out using the observed margins (OM) option in SAS MIXED procedure. The standard least square means (LSMeans) have equal coefficients across classification effects; however, the OM option changes these coefficients to be proportional to the number of patients used to calculate the classification means. This will provide LSMean estimates that are more representative of the patient population recruited in this study.

The primary treatment comparison is to compare LY2963016 versus Lantus® at the NIM of +0.4%. If the upper limit of the 95% CI on the change from baseline to 24-week endpoint HbA1c for LY2963016 versus Lantus® is below +0.4%, then LY2963016 will be declared noninferior to Lantus®. The LSMean and standard error derived from the MMRM model for each treatment will be used to test noninferiority. Type III sums of squares will be used to make the treatment comparisons.

- If the +0.4% NIM is met, a key secondary treatment comparison will be conducted to show noninferiority of Lantus® to LY2963016. This will be done by comparing Lantus® versus LY2963016 at the NIM of -0.4%. If the lower limit of the 95% CI on the change in HbA1c from baseline to the 24-week endpoint for LY2963016 versus Lantus® is above -0.4%, then Lantus® will be declared noninferior to LY2963016. The LSMean and standard error derived from the MMRM model for each treatment will be used to test noninferiority. This gate-keeping procedure controls the family-wise Type 1 error rate at a 1-sided 0.025 level.

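### SAP 5.2.12: in the two entry-HbA1c subgroup analyses the within-arm LSMeans fall at the overall mean baseline HbA1c, so they do not describe the change in the subgroup they are labelled with

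*SAP*

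**What the plan says.** SAP 5.2.12 (Subgroup Analyses) sets out to assess the consistency of the treatment effect on HbA1c. Each subgroup factor gets its own MMRM on the FAS, with treatment, visit, the stratification terms, the subgroup and its interactions with treatment and visit, and baseline HbA1c as a covariate. There is no interaction of baseline with treatment, subgroup or visit, so one slope serves all arms, levels and visits. Two of the listed factors are cuts of entry HbA1c, at 7% and at 8.5%. A factor is analysed only if its cells are large enough, with 20 patients per treatment-by-subgroup cell given as an example.

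For reporting: "The contrast from the MMRM model with the OM option using PROC Mixed in SAS above will be used to obtain the LSmeans", namely those for change in HbA1c "levels from baseline to Week 24 within each treatment at each level of the subgroup". The LSMean difference between arms is also reported, with its 95% CI and p-value.

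SAP 5.2.7 explains the option: "the OM option changes these coefficients to be proportional to the number of patients used to calculate the classification means". Its stated reason is to make the estimates more representative of the patients recruited. Neither section gives a value at which baseline HbA1c is held. Baseline is Visit 2 (SAP 5.2.1). Entry HbA1c is not defined, and the 8.5% cut matches the screening stratum in Protocol 9.3.

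**The concern.** For factors such as gender or age group, holding baseline HbA1c at one common value is ordinary adjustment. For the two entry-HbA1c factors the covariate is essentially the subgrouping variable. The PROC MIXED default sets an unspecified covariate to its overall mean, and OM as the SAP describes it does not change that. The LSMean labelled as the change in patients below 7% is then a prediction for a baseline well above theirs, and the LSMean for patients at or above 8.5% is a prediction for a baseline well below theirs. If change is roughly linear in baseline, both levels show nearly the same change whatever happened in them.

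What is at stake is how the subgroup tables are read. These are prespecified outputs that a reader will take as showing how well-controlled and poorly controlled patients fared. A rise in the first group could be printed as a fall, and a large fall in the second group would be understated.

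**Working it through.** **1. The plan's own figure.** The documents give no figure for a subgroup LSMean, a mean baseline HbA1c or a baseline slope. The figure that can be checked is the sample size, which supplies the per-arm number used below. The inputs are a margin of 0.4 on the between-arm difference, "a common standard deviation (SD) of 1.05% for change from baseline in HbA1c, a two-sided significance level of 0.05, and over 80% power", and a true difference of zero.

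- Completers per arm: 2 × (1.960 + 0.842)² × 1.05² / 0.4² = 108.2, rounded up to 109. This matches "109 completers per arm (218 total) are needed at 24 weeks".
- Power at 109 per arm: 80.3%.
- Randomized per arm: 109 / 0.85 = 128.2, rounded up to 129.

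The sample size reproduces.

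**2. Formula for the shift.** With one slope b for baseline,

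LSMean at overall mean − LSMean at subgroup mean = b × (overall mean − subgroup mean).

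The expression contains no treatment term, so it is the same in both arms and cancels from their difference.

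**3. Size.** Assumed, not in the documents: baseline normal with SD 1.1, truncated at 11% (the entry limit in Protocol 8.1); slope of change on baseline −0.1 to −0.5. Gaps and shifts are rounded separately.

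| Level | Assumed mean baseline | Overall mean after truncation | Subgroup mean | Gap | Shift at −0.1 | at −0.3 | at −0.5 |
|---|---|---|---|---|---|---|---|
| <7% | 7.5 | 7.50 | 6.29 | 1.21 | −0.12 | −0.36 | −0.61 |
| <7% | 8.0 | 7.99 | 6.41 | 1.59 | −0.16 | −0.48 | −0.79 |
| ≥8.5% | 8.0 | 7.99 | 9.20 | −1.21 | +0.12 | +0.36 | +0.60 |
| ≥8.5% | 8.5 | 8.47 | 9.33 | −0.86 | +0.09 | +0.26 | +0.43 |

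A negative shift makes the printed change look more favourable than the change at the subgroup's own baseline. A positive shift makes it look less favourable.

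**4. Simulation check.** A week-24 ANCOVA stood in for the MMRM, with treatment, subgroup, their interaction and baseline. It used N = 258, total SD of change 1.05, an overall change of about −0.3 (assumed), and only runs with at least 20 patients per cell. At mean 8.0, SD 1.1 and slope −0.3, the <7% LSMean averaged −0.29 at the overall mean baseline and +0.18 at the subgroup's own mean. The raw subgroup mean was also +0.18, so the sign reverses. The between-arm difference changed by at most about 2 × 10⁻¹⁶ in any setting, which is rounding error.

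**5. Would the analysis be run?** Twenty of 129 is 15.5% of an arm. Expected patients per arm (129 × share, SD 1.1):

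- <7%: 129 × 0.324 = 41.8 at mean 7.5; 129 × 0.182 = 23.5 at mean 8.0; 129 × 0.087 about 11 at mean 8.5. At mean 8.0, about two thirds of simulated runs met the cell condition.
- ≥8.5%: 129 × 0.323, about 42, at mean 8.0; 129 × 0.494, about 64, at mean 8.5.

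At the higher mean the <7% analysis would usually be skipped, while the 8.5% cut would still be run.

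**The case against.** The strongest reply is that nothing the section sets out to assess is harmed. Its purpose is consistency of the treatment effect, and the LSMean difference, its CI and the interaction test do not depend on where the covariate is held. This stands in full and is why the point is of low severity.

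Three stronger readings are tempting, and the documents do not support them.

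- *That the shift threatens the 0.4% margin.* SAP 5.2.7 applies the margin to the comparison of arms: "The primary treatment comparison is to compare LY2963016 versus Lantus® at the NIM of +0.4"%. A within-arm change has no margin, and the between-arm difference does not move.
- *That the LSMeans are wrong.* They are correctly computed adjusted means at a common baseline. The difficulty is that they are presented as the change at each subgroup level. The change at the subgroup's own mean has a limitation too: if entry HbA1c is the Visit 2 value, it includes regression to the mean.
- *That patients below 7% cannot have the overall mean baseline.* This needs an overall mean of at least 7%, which is not documented, and entry HbA1c taken at Visit 2. If entry means Visit 1, some patients below 7% at entry can have a Visit 2 baseline of 7% or more.

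It can also be said that the SAP never names the overall mean, so a programmer could choose another value. That is true of the text, but the procedure as specified leads to the default. Finally, the magnitude depends on an assumed slope: at −0.1 to −0.2 the <7% shift in the settings tabulated stays at about 0.1 to 0.3 points. Very large shifts also come from high mean baselines, where the cell-size condition would usually stop the <7% analysis. Both limits are accepted.

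**Conclusion.** The point holds as a reporting matter. For the two entry-HbA1c factors, the procedure in SAP 5.2.12 gives within-arm LSMeans at the overall mean baseline, and these do not describe the change in the subgroup named. The likely size is about 0.1 to 0.8 points for the <7% level and 0.1 to 0.6 for the ≥8.5% level, conditional on the assumed means, SD and slopes. Sign reversal below 7% is possible at moderate slopes, given a small overall fall. No treatment comparison and no non-inferiority or equivalence conclusion changes. The point is of low severity, but worth correcting because these tables are prespecified and easily misread.

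**What to change.** Add one sentence to SAP 5.2.12: for the two entry-HbA1c factors, the within-arm LSMeans are computed at the mean baseline HbA1c of that subgroup level, pooled over both arms (LSMEANS with the AT option, OM kept). Pooling matters. With arm-specific means, subtracting the printed LSMeans would add slope × (difference in baseline means between arms) to the treatment contrast.

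State in the same place whether entry HbA1c is the Visit 1 or the Visit 2 value. Leave the model, the between-arm difference, its CI and the interaction test as they are.

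The cost is a sentence or two in the SAP and one option in the LSMEANS statement. No further data are needed and no treatment comparison changes.
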